Visit Number	SCR	Visit 1	Visit 2	Visit 3	Visit 4	Visit 5	Visit 6	Visit 7	Visit 8	Visit 9/ EOS	a An unscheduled visit can be required due to AEs, increase in ATs, or CNS events.	b Dosing within 6 hours of disease diagnosis (at a maximum of 12 hours). c Hospitalization for 4 continuous days (72 hours post first dose). d Day 29, or day at premature discontinuation (Note: All Day 29 study evaluations will be done before antimalarial rescue treatment is provided).
Day	Day 1 (-12h) b	Day 1 (Dosing)	Day 2	Day 3	Day 4 (72h post) c	Day 8	Day 15	Day 22	Day 29 d	Day 43		
Visit Window	-	-	-	-	-	± 1 day	± 2 days	± 2 days	± 2 days	± 2 days		
												A thin blood smear should be reserved in the event of recrudescence, to confirm P. falciparum . The exact sampling timepoints during the hospitalization period are provided in Table 2.
		CCI	■	■	■	■	■	■	■	■		
CCCI			■	■	■		■	■	■	■		

Assessments & Procedures		Hospitalization					Out-patient Visits					Unscheduled Visit a	Notes
Visit Number	SCR	Visit 1	Visit 2	Visit 3	Visit 4	Visit 5	Visit 6	Visit 7	Visit 8	Visit 9/ EOS			
Day	Day 1 (-12h) b	Day 1 (Dosing)	Day 2	Day 3	Day 4 (72h post) c	Day 8	Day 15	Day 22	Day 29 d	Day 43			
Visit Window	-	-	-	-	-	± 1 day	± 2 days	± 2 days	± 2 days	± 2 days			
PK blood sampling for M5717		X	X	X	X	X	X	X	X	X		The exact sampling timepoints during the hospitalization period are provided in Table 2 . Not applicable for Pyramax (Cohort B3).	
PK blood sampling for pyronaridine		X	X	X	X	X	X	X	X	X		The exact sampling timepoints during the hospitalization period are provided in Table 2 . Not applicable for Pyramax (Cohort B3).	

CCI

ACPR= adequate clinical and parasitological response, AE=adverse event, ALP= alkaline phosphatase, ALT=alanine aminotransferase, AST=aspartate aminotransferase, AT=aminotransferase, CNS=central nervous system, DILI=drug-induced liver injury, ECG=electrocardiogram, EOS=end-of-study, PK=pharmacokinetic(s), RT-qPCR= reverse transcription quantitative real-time polymerase chain reaction, QTcF= corrected QT interval by Fridericia's formula, RT=reverse transcriptase, SCR=screening, TB=total bilirubin, ULN=upper limit of normal, WOCBP= woman of childbearing potential.

Table 2 Assessment and Sampling Timepoints During the Hospitalization Period: PK, Vital Signs, ECG, and Parasitemia

Assessment																		Notes

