## 8.1 Efficacy Assessments and Procedures

### Assessment of Primary Efficacy Endpoint

The primary efficacy endpoint of Part B of the study is defined by PCR-adjusted ACPR 28 days after first treatment (note that the primary endpoint of Part A is related to safety). ACPR is defined as absence of parasitemia (thick smear/microscopy, after adjustment for parasitemia due to new infections as determined by genotyping using PCR techniques), irrespective of axillary temperature, in participants who did not previously meet any of the criteria of ETF, LCF or LPF. ETF, LCF and LPF are defined according to WHO guidelines (WHO 2021, see also [Table 3](#)). PCR-adjusted ACPR is defined as clearance of asexual parasitemia within 7 days of initiation of study treatment and without recrudescence within 28 days of initiation of study treatment. New infection (with a different parasite stem as compared to primary infection) as evidenced by PCR genotyping studies will not be considered a treatment failure.

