#### 9.4.1.1 Efficacy Analyses Related to Primary Objective

Per ICH E9(R1), Addendum on Estimands and Sensitivity Analysis in Clinical Trials (November 2019), the primary estimand targeting the primary objective is defined by the following attributes:

- **Variable (endpoint):** The primary endpoint is the PCR-adjusted ACPR 28 days after first dose, defined as absence of parasitemia (thick smear/microscopy, after adjustment for parasitemia due to new infections as determined by genotyping using PCR techniques), irrespective of axillary temperature, in participants who did not previously meet any of the criteria of ETF, LCF, or LPF.
- **Treatment:** Intervention of interest is either a **1-day (once daily)** or a **2-day regimen (once daily)** with M5717 660/500 mg plus pyronaridine 720 mg ( $\geq 65$  kg), 540 mg ( $\geq 45$  to  $< 65$  kg), or 360 mg ( $\geq 24$  to  $< 45$  kg). A 3-day regimen (once daily) of Pyramax (pyronaridine-artesunate) 720/240 mg ( $\geq 65$  kg), 540/180 mg ( $\geq 45$  to  $< 65$  kg), or 360/120 mg ( $\geq 24$  to  $< 45$  kg) is used as internal control arm mainly for safety analyses.
- **Target Population:** The target population is defined as the population of patients targeted by the clinical question. **CCI**
- **Strategies for handling ICEs:** A composite variable strategy, i.e. the primary endpoint is considered as failure (no ACPR) is applied if participants take rescue medication after intake of study intervention or if they discontinue the study due to lack of efficacy or malaria induced death. In case participants experience any event that effects the absorption of the study intervention (e.g., vomiting within the study intervention absorptive period of 2 times median  $T_{max}$ ) or any event of immune response, a treatment policy strategy is applied as to which the treatment effect is estimated regardless of the ICE. A Principal Stratum strategy is

considered for participants with documented intake of prohibited medication that impacts the treatment effect (e.g., drug with antimalarial activity) at any timepoint.

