	
Censoring will be done at the day of the last available microscopy assessment.
 
Population-level Summary: Median parasite clearance time as estimated by Kaplan-Meier method
	
CCI		

Cohort B0:

[figure not shown]
Objectives	Estimands/Endpoints	Ref. #
Primary		
To describe clinical efficacy of the M5717- pyronaridine combination in adult and adolescent participants with acute uncomplicated malaria due to P. falciparum	
Endpoint: PCR-adjusted ACPR 28 days after first treatment (i.e., on Day 29) defined as absence of parasitemia (thick smear/microscopy, after adjustment for parasitemia due to new infections as determined by genotyping using PCR techniques), irrespective of axillary temperature, in participants who did not previously meet any of the criteria of ETF, LCF, or LPF
 
Target Population: Adult and adolescent patients with acute uncomplicated malaria due to P. falciparum
	19

	
Treatment: Single dose M5717 660/500 mg (adolescents < 45 kg) plus pyronaridine 720 mg (\geq 65 kg), 540 mg (\geq 45 to < 65 kg), or 360 mg (\geq 24 to < 45 kg)
 
Intercurrent Event Strategy:
 
• Intake of rescue medication: Composite variable strategy, i.e., endpoint is considered as treatment failure (= presence of parasitemia)• Intake of prohibited medication that impacts treatment effect (e.g., drug with antimalarial activity) at any timepoint: Treatment policy strategy, i.e., treatment effect is estimated regardless of the ICE• Experience of any event that affects absorption (i.e., vomiting within the study intervention absorptive period of $2 \times$ median t_{max}) or immune response (severe immunocompromised participants): Treatment policy strategy, i.e., treatment effect is estimated regardless of intercurrent event or Principal Stratum strategy• Premature study discontinuation due to lack of efficacy: Composite variable strategy• Death due to malaria: Composite variable strategy 
Population-level Summary: PCR-adjusted ACPR rate, i.e., proportion of participants achieving PCR-adjusted ACPR at Day 29
	
Secondary		

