14.1 Crude and PCR-adjusted ACPR at Various Timepoints

Crude ACPR 28 and 42 days after first dose is defined as absence of parasitemia (parasite count = 0) from thick smear/microscopy, irrespective of axillary temperature, in participants who did not previously meet any of the criteria of ETF, LCF, or LPF.

PCR-adjusted ACPR 28 and 42 days after first dose is defined as absence of parasitemia (parasite count = 0) from thick smear/microscopy after adjustment for parasitemia due to new infections as determined by genotyping using PCR techniques, irrespective of axillary temperature, in participants who did not previously meet any of the criteria of ETF, LCF, or LPF. By PCR-adjustment all participants with parasitemia due to a new infection are considered responders. Note that PCR-adjusted ACPR 28 days after first dose is the endpoint of the primary estimand for Part B Cohort B0.

In order to derive the population-level summary of the estimands, different intercurrent events (ICEs) will be considered. ICE as defined by the study protocol will be identified and handled as described in the following if the ICE takes place before 28 or 42 days post treatment:

- **Intake of rescue medication:** Filtering concomitant medications programmatically for all artemisinin-based combination therapies (artemether-lumefantrine, artesunate-amodiaquine, dihydroartemisinin-piperaquine, artesunate-sulphadoxine-pyremethamine), chloroquine, quinine, halofantrine, primaquine and by medical review. A composite variable strategy is applied, i.e., the primary endpoint is considered as failure (= presence of parasitemia and no ACPR).
- **Intake of prohibited medication that impacts treatment effect (e.g., drug with antimalarial activity) at any timepoint:** A treatment policy strategy is applied, i.e., treatment effect is estimated regardless of the ICE.
- **Experience of any event that affects absorption (i.e., vomiting within the study intervention absorptive period of $2 \times \text{median tmax}$) or immune response (severe immunocompromised participants):** Filter AE data programmatically for preferred term (PT) “Vomiting” within the System Organ Class (SOC) “Gastrointestinal disorders” and by medical review. A treatment policy strategy is applied, i.e., treatment effect is estimated regardless of ICE.

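### SAP 14.1 gives a treated, PCR-confirmed new infection two opposite scores in PCR-adjusted ACPR (responder, and rescue failure) and states no order of precedence

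*SAP*

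**What the plan says.** - **SAP 14.1, intercurrent events.** One list serves crude and PCR-adjusted ACPR, with events "handled as described in the following if the ICE takes place before 28 or 42 days post treatment". Rescue is found by "Filtering concomitant medications programmatically for all artemisinin-based combination therapies" and several other named antimalarials, plus medical review. The consequence is: "A composite variable strategy is applied, i.e., the primary endpoint is considered as failure (= presence of parasitemia and no ACPR". Neither the indication nor the genotype of the treated episode is a criterion.
- **SAP 14.1, PCR adjustment.** "By PCR-adjustment all participants with parasitemia due to a new infection are considered responders". No exception is made for participants who are then treated.
- **SAP section 5.** For endpoint 19, the Cohort B0 primary: "Intake of rescue medication: Composite variable strategy, i.e., endpoint is considered as treatment failure (= presence of parasitemia". Endpoints 7 and 24 take their handling from endpoint 6, which is crude ACPR. SAP section 7 records that move; the protocol had pointed to endpoint 3, where events stop at Day 4.
- **Protocol 8.1, primary endpoint.** A new infection "as evidenced by PCR genotyping studies will not be considered a treatment failure".
- **Protocol 9.4.1.1.** The composite rule "is applied if participants take rescue medication after intake of study intervention". The synopsis and Table 4 (endpoint 19) agree, again with no genotype condition.
- **SAP 14.1, prohibited medication.** A drug with antimalarial activity that is classed as prohibited medication is handled by treatment policy, so it does not alter the score.
- **Protocol 1.3, Day 29 footnote.** "All Day 29 study evaluations will be done before antimalarial rescue treatment is provided".

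**The concern.** PCR adjustment exists to separate failure to cure the initial infection from a later, unrelated one. If treating the later infection is itself scored as failure, the adjustment does nothing for that participant, who gets the same score in the crude and the PCR-adjusted analysis.

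This bears on the main efficacy result. Cohorts B1 to B3 were not enrolled (SAP section 7), so the Part B primary estimate is the Cohort B0 rate, from a planned 25 participants. At that size one reclassified participant is visible. With no precedence written down, the programmer or the medical reviewer has to choose, in an open-label study.

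**Working it through.** **Step 1. One participant through the rules.** Take someone who clears by 48 hours, has a film positive on Day 22 that is genotyped as a new strain, and is then given a listed antimalarial.

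| Rule | Result for PCR-adjusted ACPR at 28 days |
|---|---|
| Protocol 8.1, new infection | not a failure |
| SAP 14.1, PCR sentence | responder |
| SAP 14.1, rescue bullet | failure |
| SAP 14.1, if medical review calls the course prohibited medication | treatment policy, so the PCR sentence decides: responder |
| SAP 14.3/14.4, the Day 22 parasitemia itself | LCF if febrile, LPF if not; neither has a genotype condition, and either bars ACPR |
| SAP 14.3/14.4, rescue at 4 to 28 or 7 to 28 days | scored as LCF or LPF present, which bars ACPR |

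The first three rows show the conflict. The fourth shows that the result can turn on how the course is labelled. The last two show that changing the rescue bullet alone would not restore responder status.

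**Step 2. Who is reached.** For the 28-day endpoint the rule covers only treatment before 28 days. Outpatient films on Days 8, 15 and 22 leave room for such cases. A new infection first seen at the Day 29 evaluations and treated afterwards is untouched by the rescue rule for that endpoint, but is caught by it for the 42-day endpoint.

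**Step 3. The plan's own figure.** The Wilson limits without continuity correction are

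[p + z²/(2n) ± z·√(p(1−p)/n + z²/(4n²))] / (1 + z²/n), with z = 1.96.

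With p = 0.95 and n = 50 the lower limit is 85.1% (85.3% averaged over the binomial distribution). This reproduces the synopsis figure of about 85%.

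**Step 4. Cohort B0, n = 25.** Assume 24 responders when treated new infections count as responders, and let the rescue rule turn k of them into failures. Each costs 1/25 = 4 points.

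| k (assumed) | Rate | Wilson 95% CI |
|---|---|---|
| 0 | 24/25 = 96% | 80.5 to 99.3 |
| 1 | 23/25 = 92% | 75.0 to 97.8 |
| 2 | 22/25 = 88% | 70.0 to 95.8 |
| 3 | 21/25 = 84% | 65.3 to 93.6 |
| 4 | 20/25 = 80% | 60.9 to 91.1 |

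**Step 5. Chance that it arises.** For an assumed risk r of a new infection treated before 28 days, the chance of at least one case among 25 is 1 − (1 − r)^25. This is 40% for r = 2%, 72% for r = 5% and 93% for r = 10%. The documents give no value for r.

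**The case against.** The strongest reply is that the SAP implements the protocol's primary estimand, which makes rescue a failure without any genotype condition in the synopsis, Table 4 and 9.4.1.1. That stands. The SAP disagrees with Protocol 8.1 but agrees with those three places, so the inconsistency is within the protocol and both documents need reconciling.

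Second, treating a new infection may not be rescue at all. Protocol 6.6 ties rescue to the intervention failing to cure, and the circumstances listed in 6.8.1 end at Day 8. Medical review could therefore class a Day 22 course as prohibited medication. This also stands, so failure is the literal reading but not the only one. It does not settle the matter: the Schedule of Activities allows rescue as required, the SAP filter works by drug name, and nothing written tells the reviewer which label applies.

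Third, scoring such a participant as a responder has a cost. After rescue the initial infection can no longer be observed, so success may be overstated, and the unconditional rule is the conservative one. That is a reason to keep it as a sensitivity analysis.

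Fourth, few participants may be affected. The protocol background describes liver-stage activity and prolonged protection for M5717, which points toward fewer new infections. This is fair; the count is unknown.

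**Conclusion.** The point holds as an unresolved conflict in the scoring of the Cohort B0 primary endpoint and of endpoints 7 and 24. Two rules in one section give opposite answers for a treated, genotype-confirmed new infection. The literal result of the rescue rule is contrary to Protocol 8.1. The size is 4 points per affected participant, for an assumed number of participants.

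A reader might infer more than the documents support:

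- **That the SAP departs from the protocol.** It carries over a conflict already there.
- **That PCR-adjusted ACPR collapses to crude ACPR, or that the estimate tracks local transmission.** The two coincide only for new infections that are treated before the timepoint and labelled rescue. No new-infection rate is given, and the documents do not show how many would be treated in that window.
- **That the rescue bullet alone costs 4 points each under the present text.** The same parasitemia already meets the LCF or LPF definition as written. The effect must not be counted again with any separate point about genotype in LCF and LPF.

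**What to change.** 1. In SAP 14.1 and SAP section 5 (endpoints 7, 19, 24), for PCR-adjusted ACPR only: rescue counts as failure unless the parasitemia on the last film before rescue is genotyped as a new infection after documented clearance of the initial infection. That participant is then classified by the PCR sentence. Indeterminate or missing genotype stays failure.
2. When deriving PCR-adjusted ACPR, apply the same condition to the clause on previously met LCF or LPF, including LCF or LPF imputed from rescue. Leave crude ACPR and the stand-alone LCF and LPF rates unchanged.
3. Record the change in SAP section 7, and reconcile the protocol synopsis, Table 4 (endpoint 19) and 9.4.1.1 with Protocol 8.1. If data review has already taken place, SAP section 4 requires the change to be labelled as such in the study report.
4. Report how many participants are affected, and show the unconditional rule as a sensitivity analysis. Censoring at the new infection could be a second.

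The cost is SAP and protocol wording plus one derivation, using genotyping that Protocol 8.1 already plans. The drawback is that the initial infection is unobserved after rescue, which is why step 4 is needed. The change affects scoring only, not who is treated or how.

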14.2 Early Treatment Failure (ETF)

ETF is defined as meeting any of the following:

- a) Danger signs or severe malaria 1, 2, or 3 days after treatment (i.e., between Days 2 and 4), in the presence of parasitemia (parasite count > 0).
- b) Parasitemia 2 days after treatment higher than on day of treatment (defined as count at baseline), irrespective of axillary temperature.
- c) Parasitemia 3 days after treatment with temperature $\geq 37.5^{\circ}\text{C}$.
- d) Parasitemia 3 days after treatment $\geq 25\%$ of parasite count on day of treatment (defined as the count at baseline).

The same ICEs and strategies as defined for ACPR (see Section 14.1) will be applied for ETF, however, limited to events that occur before or at Day 4 (i.e., 3 days after treatment). Failure is considered presence of ETF.

The population-level summary is proportion of participants with ETF (ETF rate). ETF rate will be estimated with 95% confidence intervals. Confidence intervals will be derived by use of Wilson's score method.

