8.1 Definition of Analysis Sets

The following Analysis Sets will be used:

Full Analysis Set (FAS)

The FAS will include all enrolled participants. Participants will be analyzed according to the treatment assigned at enrollment as per the Intention-to-Treat principle.

Safety Analysis Set (SAF)

All participants, who were administered any dose of any study intervention. Analyses will consider participants as treated.

PK Analysis Set (PKAS)

All participants, who receive ≥ 1 dose of study intervention, have no clinically important protocol deviations or important events affecting PK, and provide ≥ 1 measurable post-dose concentration. Participants will be analyzed per the actual study intervention they received. All PK analyses will be based on this analysis set for the final analysis.

Note that important protocol deviations or important events that lead to exclusion of participants from the PK Analysis Set are identified during the data review process.

The following table summarizes the use of the analysis sets in the different analyses.

Analyses	Analysis Set		
	FAS	SAF	PK Analysis Set
Baseline Characteristics	✓	✓*	
Previous and Concomitant Therapies	✓	✓*	
Efficacy: Primary Endpoint/Estimand	✓		
Efficacy: Secondary Endpoint/Estimand	✓		
Efficacy: CCI Endpoints/Estimands	✓		
Safety and Tolerability		✓	
PK analyses			✓

*only to be created if discordance between FAS and SAF is more than 5%

In addition to the above defined sets used for analysis, the Screened Analysis Set will be used only for the disposition table. The Screened Analysis Set contains all subjects who signed the informed consent.

9 General Specifications for Data Analyses

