9.3 Presentation of Tables/Listings/Figures

Tables and Figures will be presented by Part, unless otherwise specified. A “Total” column will be included in non-efficacy tables. In the individual participant data listing all individual data will be listed as measured. Unless otherwise specified, all listings will be sorted by Part, M5717 dose, subject ID, and scheduled time point.

Repeated and unscheduled measurements included in the listings will not be used for statistical analyses or summaries, unless the repeated measurement was performed due to unreliable values/technical reasons, e.g., clotted samples. They will be flagged as such in the listings.

Presentation of continuous and qualitative variables

Unless otherwise specified, continuous variables will be summarized using descriptive statistics, i.e., the number of participants with non-missing values (n), the number of participants with missing values (nmiss), mean, standard deviation, median, 25th percentile (Q1) and 75th percentile (Q3), minimum, and maximum.

Qualitative variables will be summarized by frequency counts and percentages. Unless otherwise stated the calculation of proportions will be based on the number of participants of the analysis set of interest. Therefore, counts of missing observations will be included in the denominator and presented as a separate category.

Descriptive statistics by nominal visit or time point, e.g., for laboratory measurements, will include only data from scheduled visits.

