9.13 Imputation of Missing Data

No action will be taken to handle missing data. A participant who withdraws prior to the last planned observation in a study period will be included in the analyses up to the time of discontinuation.

Unless otherwise specified, all data will be evaluated as observed, and no imputation method for missing values will be used.

To determine treatment-emergent AEs, incomplete AE-related start dates will be imputed as follows:

- In case the onset date is missing completely or missing partially but the onset month and year, or the onset year, are equal to the start of study intervention then the onset date will be imputed by the minimum of start of study intervention and AE resolution date (if not missing). If AE resolution date is completely or partially missing, then the study intervention date will be used.
- In all other cases, the missing onset day or missing onset month will be imputed by 1.

Incomplete or missing AE stop dates will not be imputed, since no durations of AEs are planned to be derived.

Missing or partially missing dates for Medical History will not be imputed.

In order to allocate medications to either previous or concomitant, the following imputation rules for (partially) missing start dates will be applied:

- If the day is missing, it will be imputed by the 1st day of the month.
- If both day and month are missing the date will be imputed by 1st January.
- If the date is completely missing, no imputation will be performed.

10 Study Participants

The subsections in this section include specifications for reporting participant disposition and study intervention/study discontinuations. Additionally, procedures for reporting protocol deviations are provided.

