14.3 Late Clinical Failure (LCF)

LCF is defined as meeting any of the following:

- a) Danger signs or severe malaria in the presence of parasitemia on any day between 4 and 28 days after treatment (i.e., between Days 5 and 29) in participants who did not previously meet any of the criteria of ETF.
- b) Presence of parasitemia on any day between 4 and 28 days after treatment with temperature $\geq 37.5^{\circ}\text{C}$ in participants who did not previously meet any of the criteria of ETF.

The same ICEs and strategies as defined for ACPR (see Section 14.1) will be applied for LCF, however, limited to events that occur between 4 and 28 days after treatment (i.e., between Days 5 and 29). Failure is considered presence of LCF.

The same analyses and population-level summaries as described for ETF will be applied for LCF.

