15.6 Other Safety or Tolerability Evaluations

15.6.1 ECG Evaluations

The following analyses will be performed for each 12-lead ECG parameter (RR, PR, QRS, QT, ventricular rate -denoted as HR in what follows-, and QTcF):

- Descriptive statistics at baseline, at each post-baseline time point and changes from baseline at each post-baseline time point
- Frequency (number and percentage) of participants with notable ECG values according to the following categories by analysis visit.
 - QT/QTcF >450 ms, >480 ms, >500 ms
- ECG interpretation (normal, abnormal/not clinically significant, abnormal/clinically significant) will be summarized at Baseline and during the on-treatment period.

- A graphical display, boxplots of change from baseline for ECG parameters will be provided in addition.

Complete ECG profiles will be provided for participants with at least one notable ECG value (related to ECG interpretation) as defined above (i.e. abnormal clinically significant, abnormal not clinically significant). For these participants, all ECG parameter values collected during the study will be provided.

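### Missing films enter the ETF, LCF and LPF rates as non-failures, so these rates can only err low; the SAP needs a missing-counted-as-failure bound

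*SAP*

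**What the plan says.** SAP 9.3 sets the default for qualitative variables: unless otherwise stated, "the calculation of proportions will be based on the number of participants of the analysis set of interest", and "counts of missing observations will be included in the denominator and presented as a separate category". Efficacy uses the Full Analysis Set (FAS), and SAP 8.1 defines it: "The FAS will include all enrolled participants". SAP 9.13 adds that "all data will be evaluated as observed, and no imputation method for missing values will be used".

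SAP 14.1 gives ACPR its own rule. A participant with no earlier failure, no intercurrent event and no film at the ACPR timepoint stays in the denominator as N/A, and so is not a responder.

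SAP 14.2 gives the ETF measure ("The population-level summary is proportion of participants with ETF (ETF rate") and a Wilson interval, with no missing-film rule. SAP 14.3 says "The same analyses and population-level summaries as described for ETF will be applied for LCF", and 14.4 says the same for LPF. In each section three intercurrent events count as failure without a qualifying film, if they fall in that endpoint's window: rescue medication, study discontinuation for lack of efficacy, and death due to malaria.

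For ECGs, SAP 15.6.1 plans: "Frequency (number and percentage) of participants with notable ECG values according to the following categories by analysis visit". The categories are QT/QTcF above 450, 480 and 500 ms. No denominator is given, so SAP 9.3 applies here too, on the Safety Analysis Set.

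**The concern.** The same denominator rule acts in opposite directions on good and bad outcomes. For a response rate, keeping missing participants in the denominator is conservative. For a failure rate it is favourable to the drug, because a missing participant can add to N but not to the failures. The SAP does not acknowledge this, and it plans no missing-data sensitivity analysis for these endpoints.

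Missing data are foreseeable. LCF runs from Day 5 and LPF from Day 8, both to Day 29, and after the hospital stay both rest on outpatient visits. SAP 10.1 provides a row for enrolled but untreated participants, who belong to the FAS. SAP 9.4 reclassifies out-of-window assessments as unscheduled, subject to case-by-case reallocation at data review, and SAP 9.3 generally keeps unscheduled measurements out of the analyses.

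ETF, LCF and LPF are secondary efficacy endpoints in Part A and Cohort B0. SAP Section 7 attributes early termination to compelling efficacy and safety, so readers will look at these rates and their upper limits.

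**Working it through.** **Inputs.** N = 25 for Cohort B0 and N = 12 for Part A (Protocol 1.1). Wilson score interval, two-sided 95% (SAP 14.2), z = 1.96. The numbers of losses and failures are assumptions.

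**Interval formula.** With p = x/n: [p + z²/2n ± z√(p(1−p)/n + z²/4n²)] / (1 + z²/n).

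**The plan's own figure.** Protocol 1.1 expects a lower limit of about 85% for n = 50 and a 95% response rate. The formula gives 85.1% to 98.4%, so the figure reproduces.

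**Three treatments of the same data.** Let x be observed failures and m the participants lost with no earlier failure and no composite event. The SAP rule is x/N, observed only is x/(N − m), and missing counted as failure is (x + m)/N.

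| Cohort B0, N = 25 | SAP rule | Observed only | Missing = failure |
|---|---|---|---|
| m = 2, x = 1 | 1/25 = 4.0% (0.7–19.5) | 1/23 = 4.3% (0.8–21.0) | 3/25 = 12.0% (4.2–30.0) |
| m = 2, x = 2 | 2/25 = 8.0% (2.2–25.0) | 2/23 = 8.7% (2.4–26.8) | 4/25 = 16.0% (6.4–34.7) |
| m = 3, x = 0 | 0/25 = 0% (0–13.3) | 0/22 = 0% (0–14.9) | 3/25 = 12.0% (4.2–30.0) |
| m = 3, x = 2 | 2/25 = 8.0% (2.2–25.0) | 2/22 = 9.1% (2.5–27.8) | 5/25 = 20.0% (8.9–39.1) |

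In the last row the shift is 9.1 − 8.0 = 1.1 points against those observed, and 20.0 − 8.0 = 12.0 points if all three failed. The gap between the first and third columns is always m/N: 4.0 points per lost participant in Cohort B0 (1/25) and 8.3 in Part A (1/12). With no observed failures the SAP point estimate matches the observed-only one, and only the upper limit is too low.

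**Expected size if loss is unrelated to outcome.** If a fraction q of participants has no usable films, the expected rate is p(1 − q). For a true 10% it is 9.6%, 9.2%, 8.8% and 8.0% at q = 4%, 8%, 12% and 20%. For a true 20% and N = 25, the chance that the upper limit falls below the truth is 2.7% with nothing missing, 4.1% at q = 8% and 7.4% at q = 20%.

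**Would an observed-only denominator cure this?** LCF and LPF count a failure on any day in the window. Assume a true 20% failing by Day 29, half of them by Day 15, and 12% lost at random at Day 15.

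- Observed failures: 0.10 + 0.10 × 0.88 = 18.8%. This is the SAP rate, 1.2 points low.
- Non-failures with complete films: 0.80 × 0.88 = 70.4%.
- Observed-only rate: 0.188/(0.188 + 0.704) = 21.1%, which is 1.1 points high, because early failures are kept and film-negative dropouts are removed.
- Missing = failure: 0.188 + (1 − 0.188 − 0.704) = 29.6%, an upper bound.
- Kaplan-Meier, censoring at loss: 1 − 0.90 × (0.80/0.90) = 20.0%, correct when loss is random.

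**The case against.** The case for leaving the plan alone has force. Missing counts are displayed, so a careful reader can see them. The composite events already turn some of the most informative losses into failures. These are descriptive secondary rates in two non-randomised cohorts of a terminated study with no group comparison. One or two random losses among 25 move the rate by less than a point, against an interval as wide as 2.2 to 25.0. Using the FAS follows Protocol 9.3 and 9.4, and the observed-only alternative is biased upward by about as much. All of this stands. It rules out replacing the denominator, but it does not supply a bound for losses that the composite events miss, such as loss to follow-up or withdrawal for another reason.

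Three stronger readings are tempting and are not supported.

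- *ACPR and failure rates cannot be reconciled.* They can. In the example with 3 lost and 2 LPF, crude Day 29 ACPR 20/25, LPF 2/25 and N/A 3/25 make 80 + 8 + 12 = 100%. Putting 2/22 beside the other two would give 101.1%. PCR-adjusted ACPR need not add up with LPF in any case, because new infections count as responders (SAP 14.1).
- *Every participant with a missing film also lowers ACPR.* Only a film missing at the ACPR timepoint does so. A participant who misses a Day 4 or Day 15 film but is negative on Day 29 can still be a responder.
- *ETF in Part A is materially understated.* At the pessimistic 40% in Protocol 2.3.1, 2 of 12 missing would give 4/12 = 33.3% (13.8–60.9) against 4/10 = 40.0% (16.8–68.7), nearly 7 points. But ETF is assessed over 72 inpatient hours with films scheduled about every 6 hours (Protocol 8.1, Table 2), so two unassessable participants are unlikely unless many films are set aside as out of window.

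**Conclusion.** The point holds as a one-sided weakness in a stated rule. Under SAP 9.3 with the FAS, a participant with missing films and no composite event counts as a non-failure in the ETF, LCF and LPF rates and their Wilson intervals. Relative to complete data these rates can be right or too low, never too high. LCF and LPF are the most exposed and ETF the least.

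With 3 of 25 lost and 2 observed failures, the shift is about 1 point if loss is unrelated to outcome and 12 points if all three failed. Both figures rest on assumed losses. With complete follow-up the issue disappears.

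The by-visit QTcF percentages are diluted by the same arithmetic. Safety uses dosed participants, so never-treated participants play no part. The scheduled post-dose ECGs are at 2, 4, 8 and 72 hours and Day 29, so Day 29 is where dilution is most likely.

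**What to change.** In SAP 14.2 to 14.4:

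1. Keep the FAS rate with its Wilson interval as the main analysis.
2. Say which films must be present to rule out each failure. For LCF and LPF, the absence of the Day 29 film in a participant with no earlier failure would match the N/A category of crude Day 29 ACPR. Say also how a single missed visit is handled.
3. Show the missing count beside each rate.
4. Add a row counting missing as failure, with its Wilson interval. Label each row as a separate upper bound: one lost participant may enter both the LCF and LPF rows, so they must not be added.
5. Optionally add, as supportive only, an observed-only row or, for LCF and LPF, a Kaplan-Meier estimate censoring at the last film, saying how an earlier failure of another type is treated. Neither should replace the FAS rate.

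In SAP 15.6.1, base the by-visit percentages above 450, 480 and 500 ms on participants with an ECG value at that visit, and show how many have none.

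The cost is a few SAP sentences and extra table rows. No new data are needed and the analysis set does not change. When films are missing, the reported failure bound becomes less favourable.
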